### 4.2 Inclusion Criteria

Participants must meet *all* the following criteria to be eligible for the study:

1. Adult males or females aged  $\geq 18$  to  $\leq 65$  years at screening (according to country/local regulations)
2. BMI  $\leq 32$  kg/m^2
3. Able to provide informed consent indicating they understand the purpose of, and procedures required, for the study and are willing to participate
4. If female, willing not to become pregnant up to 8 weeks after last dose of study vaccine and up to 5 months after the last dose of nivolumab
5. If female: Not pregnant or breast feeding and one of the following:
  - Of non-childbearing potential (i.e. women who have had a hysterectomy or tubal ligation or are post-menopausal, as defined by no menses in  $\geq 1$  year and without an alternative medical cause)
  - Of childbearing potential but agrees to practice highly effective contraception for 4 weeks prior to study vaccine and 8 weeks after study vaccine and 5 months after the last dose of nivolumab. Highly effective methods of contraception include one or more of the following:
    - Male partner who is sterile (medically effective vasectomy) prior to the female participant's entry into the study and is the sole sexual partner for the female participant
    - Combined (oestrogen and progestogen containing) hormonal contraception associated with inhibition of ovulation:

- oral
  - intravaginal
  - transdermal
  - Progestogen-only hormonal contraception associated with inhibition of ovulation:
    - oral
    - injectable
    - implantable
  - An intrauterine device
  - Bilateral tubal occlusion
6. Documented evidence of chronic HBV infection (e.g. HBsAg positive  $\geq 6$  months with detectable HBsAg levels at screening)
  7. Receipt of only either entecavir, tenofovir (tenofovir alafenamide fumarate or tenofovir disoproxil fumarate), or besifovir for at least 12 months before screening
  8. Virally suppressed (HBV-DNA viral load below 40 IU/mL for  $\geq 1$  year)
  9. HBsAg levels  $< 4000$  IU/mL

### 4.3 Exclusion Criteria

Participants who meet *any* of the following criteria are not eligible for the study:

1. Presence of any significant acute or chronic, uncontrolled medical/psychiatric illness
2. Hepatitis C virus antibody positive.
3. HIV antibody positive
4. Co-infection with hepatitis D virus (HDV)
5. Documented cirrhosis or advanced fibrosis indicated by a liver biopsy within 6 months prior to screening (Metavir activity grade A3 and stages F3 and F4; Ishak stages 4 – 6).  
In the absence of a documented liver biopsy, either 1 of the following (not both):
  - Screening Fibroscan with a result  $> 9$  kilopascals (kPa) (or the equivalent) within  $\leq 6$  months of screening, OR
  - Screening FibroTest  $> 0.48$  and AST to platelet ratio index (APRI) of  $> 1$ .
6. ALT  $> 3 \times$  ULN, international normalized ratio (INR)  $> 1.5$  unless the participant was stable on an anticoagulant regimen affecting INR, albumin  $< 3.5$  g/dL, direct bilirubin  $> 1.5$  ULN, platelet count  $< 100,000/\mu\text{L}$ .
7. A history of liver decompensation (e.g. ascites, encephalopathy or variceal haemorrhage)
8. Prior hepatocellular carcinoma
9. Chronic liver disease of a non-HBV aetiology
10. History or evidence of autoimmune disease or known immunodeficiency of any cause
11. Presence of active infection
12. Evidence of interstitial lung disease, active pneumonitis, myocarditis, or a history of myocarditis
13. Past history of thyroid disorder or abnormal thyroid function at screening that is still active and uncontrolled

14. Prolonged therapy with immunomodulators (e.g. corticosteroids such as prednisone > 10 mg/day) or biologics (e.g. monoclonal antibodies, IFN) within 3 months of screening
15. Receipt of immunoglobulin or other blood products within 3 months prior to enrolment
16. Receipt of any investigational drug or vaccine within 3 months prior to screening
17. Receipt of any adenoviral-based vaccine within 3 months prior to administration of ChAdOx1-HBV on Day 0, or plan to receive an adenoviral-based vaccine within 3 months after Day 0
18. Receipt of any live vaccines within 30 days prior to screening
19. Receipt of any inactivated vaccines within 14 days prior to screening
20. History of severe hypersensitivity or anaphylactic reactions likely to be exacerbated by any component of the vaccine or nivolumab
21. Malignancy within 5 years prior to screening with the exception of specific cancers that are cured by surgical resection (e.g. except basal cell skin carcinoma of the skin and cervical carcinoma). Participants under evaluation for possible malignancy are not eligible
22. Current alcohol or substance abuse judged by the Investigator to potentially interfere with participant safety and compliance
23. Significant cardiac disease or unstable uncontrolled cardiac disease
24. Any laboratory test which is abnormal, and which is deemed by the Investigator to be clinically significant.
25. Cytotoxic agents, other anti HBV or traditional herbal medicines which, in the opinion of the Investigator, may have activity against HBV within the previous 6 months prior to randomization
26. Any other finding that, in the opinion of the Investigator, deems the participant unsuitable for the study

#### ***4.3.1 Removal of Participants from Therapy or Assessment***

##### *4.3.1.1 Contraindications to Vaccination*

The following events constitute contraindications to administration of study vaccine at that point in time; if any one of these events occurs at the time scheduled for vaccination, the participant may be vaccinated within 28 days of the scheduled time, or withdrawn from the study at the discretion of the Investigator.

- Acute disease at the time of vaccination. Acute disease is defined as the presence of a moderate or severe illness with or without fever. All study vaccines can be administered to participants with a minor illness such as diarrhoea, mild upper respiratory infection with or without low-grade febrile illness
- Temperature of >37.5°C (100.4°F) at the time of vaccination

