### ***3.1.4 Individual Stopping Rules (All Vaccinated Study Participants)***

In addition to the above stated group holding rules, stopping rules for individual participants will apply (i.e. in addition to withdrawal of individuals from a second vaccination). Study participants who present with at least one of the following stopping rules will be withdrawn from further vaccination in the study:

- **Local reactions:** injection site ulceration, abscess or necrosis
- **Laboratory AEs:**
  - The participant develops a Grade 3 laboratory adverse event considered possibly, probably or definitely related within 7 days after vaccination and persisting continuously at Grade 3 for >72 hours
- **Systemic solicited adverse events:**
  - The participant develops a Grade 3 systemic solicited adverse event considered possibly, probably or definitely related within 2 days after vaccination (day of vaccination and one subsequent day) and persisting continuously at Grade 3 for >72 hours
- **Unsolicited adverse events:**
  - The participant has any Grade 3 adverse event considered possibly, probably or definitely related to vaccination, persisting continuously at Grade 3 for >72 hours
  - The participant has an SAE considered possibly, probably or definitely related to vaccination
  - The participant has an acute allergic reaction or anaphylactic shock following the administration of vaccine investigational product

If the participant has an acute illness (moderate or severe illness with or without fever) or a fever (oral temperature > 37.5°C) at the scheduled time of administration of investigational product, the participant will not receive the vaccine at that time. The vaccine may be administered to that participant at a later date within the time window specified in the protocol or the participant may be withdrawn from the study at the discretion of the Investigator.

All vaccinated participants will be followed for safety until resolution or stabilisation (if determined to be chronic sequelae) of their SAEs.

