**Contains Nonbinding Recommendations**

Vital Signs *	Mild (Grade 1)	Moderate(Grade 2)	Severe (Grade 3)	Potentially Life Threatening (Grade 4)
Fever (°C) ** (°F) **	38.0 – 38.4 100.4 – 101.1	38.5 – 38.9 101.2 – 102.0	39.0 – 40 102.1 – 104	> 40 > 104
Tachycardia - beats per minute	101 – 115	116 – 130	> 130	ER visit or hospitalization for arrhythmia
Bradycardia - beats per minute***	50 – 54	45 – 49	< 45	ER visit or hospitalization for arrhythmia
Hypertension (systolic) - mm Hg	141 – 150	151 – 155	> 155	ER visit or hospitalization for malignant hypertension
Hypertension (diastolic) - mm Hg	91 – 95	96 – 100	> 100	ER visit or hospitalization for malignant hypertension
Hypotension (systolic) - mm Hg	85 – 89	80 – 84	< 80	ER visit or hospitalization for hypotensive shock
Respiratory Rate – breaths per minute	17 – 20	21 – 25	> 25	Intubation

\* Subject should be at rest for all vital sign measurements.

\*\* Oral temperature, no recent hot or cold beverages or smoking.

\*\*\* When resting heart rate is between 60 – 100 beats per minute. Use clinical judgement when characterizing bradycardia among some healthy subject populations, for example, conditioned athletes.

Systemic (General)	Mild (Grade 1)	Moderate(Grade 2)	Severe (Grade 3)	Potentially Life Threatening (Grade 4)
Nausea/vomiting	No interference with activity or 1 – 2 episodes/24 hours	Some interference with activity or > 2 episodes/24 hours	Prevents daily activity, requires outpatient IV hydration	ER visit or hospitalization for hypotensive shock
Diarrhea	2 – 3 loose stools or < 400 gms/24 hours	4 – 5 stools or 400 – 800 gms/24 hours	6 or more watery stools or > 800gms/24 hours or requires outpatient IV hydration	ER visit or hospitalization
Headache	No interference with activity	Repeated use of non-narcotic pain reliever > 24 hours or some interference with activity	Significant, any use of narcotic pain reliever or prevents daily activity	ER visit or hospitalization
Fatigue	No interference with activity	Some interference with activity	Significant, prevents daily activity	ER visit or hospitalization
Myalgia	No interference with activity	Some interference with activity	Significant, prevents daily activity	ER visit or hospitalization

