2.0 Change History

Version/Date	Change Log
1.0 16-Sep-2020	Created as new
1.1 19-Aug-2022	
Added partial AE imputation for determining if unsolicited AEs fall within 28 days of each vaccination
 
Changed the HBV DNA summary table from fold change from baseline to number and percentage of participants in each category
 
Removal of HBpgRNA and HBcrAg exploratory analyses
 
Addition of ICS and ELISpot definitions and analyses
 
Actual dose of nivolumab in mg/kg will be derived using baseline weight as weight is only collected at screening not at each visit
 
Added source of vital signs toxicity grading
 
Added visit windows for local/systemic reactogenicity
 
Updated list of laboratory parameters based on data received
 
Added list of DMC outputs to the appendix
 
Added laboratory toxicity grade appendix

1.2 09-Dec-2022	
Updated for Dry run 2 comments
 
Added HBsAg repeated measures analysis
 
Removed Kaplan-Meier analysis of HBeAg and HBsAg loss
 
Updated the seroconversion definitions
 
Added ICS and ELISpot analyses using non-parametric tests
 
Removed analyses for Month 3 boost (as no participants had the Month 3 boost)
 
Changed solicited AE analyses to combine the investigator (CRF) and eDiary data into a single analysis and removed the visit windowing for local/systemic reactogenicity
 
Added ALT and AST summary by time point

2.0 05-Jan-2023	
Up-versioned for signature
 
Updated ELISpot responder definition

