10.5.5.1 Handling of Solicited AE (eDiary) data

Solicited adverse events are recorded in the eDiary for 7 days post-vaccination (Day 0 to Day 7, Day 28 to Day 35, and Month 3 to Month 3 + 7 days [only applicable for booster participants]). All solicited AEs are considered causally related to the study treatment.

Solicited local symptoms including pain, induration (swelling), warmth, and erythema (redness), and solicited systemic symptoms including feverishness, chills, myalgia (muscle ache), fatigue (tiredness), headache, nausea, arthralgia (joint ache), and malaise (a general feeling of unwell) will be reported in a standardised manner over a period of 7 consecutive days after vaccination.

These solicited AEs and their intensity grades are based on the Food and Drug Administration (FDA) Guidance on Toxicity Grading Scale as described in Appendix 1 of the Protocol. If induration (swelling) or erythema (redness) are recorded as < 25mm in diameter in the eDiary, then this will be categorised as no event (grade 0) for the purpose of analysis. Derived intensity grades for induration and erythema are done based only on the numeric value of the parameter assessed, and clinical signs and symptoms will not be considered.

In addition, oral temperature will also be recorded for 7 days post-vaccination. Fever is defined as oral temperature $\geq 38^{\circ}\text{C}$ and the intensity grades are derived as specified in Appendix 1 of the Protocol.

Solicited AEs with missing intensity will not be included in the 'Any' count of the respective solicited AE.

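### Protocol 4.3.1.1 prints one dosing-day temperature limit as two values 0.5°C apart: 37.5°C is 99.5°F, not 100.4°F

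*Protocol*

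**What the plan says.** Section 4.3.1.1 of the protocol lists two events that stop a study vaccine being given at that moment. One is acute disease; the other is "Temperature of >37.5°C (100.4°F) at the time of vaccination". Either is enough alone: the rule applies "if any one of these events occurs at the time scheduled for vaccination". The participant may then be vaccinated within 28 days of the scheduled time or be withdrawn at the Investigator's discretion.

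Section 3.1.4 addresses the same decision. It withholds the vaccine from a participant with acute illness or "a fever (oral temperature > 37.5°C) at the scheduled time of administration of investigational product". It gives no Fahrenheit value.

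Two other places give a fever threshold for a different purpose, the grading of events after vaccination. The vital-signs table in Appendix 1 starts Grade 1 fever with the Celsius and Fahrenheit ranges "38.0 – 38.4 100.4 – 101.1". SAP Section 10.5.5.1, in the sentence that begins "Fever is defined as oral temperature", sets the threshold at 38°C or above.

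**The concern.** A limit that decides whether a dose is given should return one answer for one reading. The two figures in 4.3.1.1 are presented as the same temperature in two units, and they are not. Staff who apply the Celsius figure would defer a participant whom staff applying the Fahrenheit figure would vaccinate.

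The stake is a dose deferred by up to 28 days, or a discretionary withdrawal, on one reading of the line, against vaccination on schedule on the other. The line is current operative text, not part of an amendment log.

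**Working it through.** **Inputs**

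- Protocol 4.3.1.1: limit of 37.5°C, bracket of 100.4°F.
- Protocol 3.1.4: oral limit of 37.5°C, Celsius only.
- Protocol Appendix 1, vital signs: the Grade 1 fever range begins at 38.0°C, paired with 100.4°F.

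**Formulas**

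F = C × 9/5 + 32, and C = (F − 32) × 5/9.

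**Trying to reproduce the bracket**

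- From the printed Celsius limit: 37.5 × 9/5 + 32 = 67.5 + 32 = 99.5°F. The printed 100.4°F is not reproduced.
- From the printed bracket: (100.4 − 32) × 5/9 = 68.4 × 5/9 = 38.0°C. Only a Celsius limit of 38.0 gives the bracket.

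**Size of the gap**

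- 100.4 − 99.5 = 0.9°F.
- 38.0 − 37.5 = 0.5°C.

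**Could it be rounding?** No. Both conversions are exact to one decimal. In the Appendix 1 fever row the printed pairs agree with the formula to within 0.1°F: 38.5°C converts to 101.3°F and is printed as 101.2, and 39.0°C converts to 102.2°F and is printed as 102.1. The gap here is 0.9°F.

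**What each figure does to a reading**

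| Dosing-day reading | Limit of 37.5°C | Limit of 100.4°F (38.0°C) |
|---|---|---|
| 37.5°C or below | no deferral | no deferral |
| above 37.5°C, up to 38.0°C | deferral | no deferral |
| above 38.0°C | deferral | deferral |

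**Which figure is the likely slip?** Section 3.1.4 independently gives 37.5°C for the same decision, and the Celsius figure comes first in 4.3.1.1. The bracketed 100.4°F coincides with the 38.0°C fever boundary used for grading in Appendix 1 and in the SAP, which is a plausible source for a misplaced number. The grading thresholds do not conflict with a 37.5°C dosing limit, because they serve another purpose; they only confirm the conversion.

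**The case against.** The best case on the other side accepts the arithmetic and disputes the weight.

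- **The limit can be recovered.** Section 3.1.4 repeats 37.5°C, and Fahrenheit appears in 4.3.1.1 only as a gloss. This is right, and it is why the bracket is called the likely error.
- **Staff probably worked in Celsius.** Centres are planned in South Korea, Taiwan and the UK, and the other operative temperature limits in the protocol and SAP are in Celsius. Nothing shows a centre using the Fahrenheit figure. This also stands and limits the importance of the point.
- **The Celsius figure might be the wrong one.** The acute-disease bullet in 4.3.1.1 permits vaccination in minor illness even with a slight fever, and that allowance has more room under a 38.0°C cut-off. This is fair evidence against certainty, but it does not outweigh the explicit 37.5°C in 3.1.4. The mismatch is certain; the choice between the two values is only probable, so the sponsor has to confirm it.
- **The two sections are not worded identically.** Section 3.1.4 specifies an oral reading, while 4.3.1.1 names no route. This slightly weakens the inference about intent but has no bearing on the conversion.
- **It may be too late to matter.** If dosing has finished, the correction changes nothing in conduct. It would still settle which limit applies if a past reading between the two values were queried.

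**Conclusion.** The point holds. Section 4.3.1.1 gives a single dosing limit as two temperatures that differ by 0.5°C (0.9°F), and readings above 37.5°C and up to 38.0°C get opposite answers. That the figures disagree needs no assumption. That the bracket is the wrong one is a judgement resting mainly on Section 3.1.4.

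The practical effect is small. It arises only for readings in that band, and only where someone applied the Fahrenheit figure. The documents do not say whether any participant had such a reading. No effect on participants, analysis sets or results is shown, and the sample size and endpoint analyses do not use this number. It is a minor correction worth considering.

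**What to change.** Ask the sponsor to confirm the intended limit, then make one of two changes:

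- **If 37.5°C was meant (more likely):** change the bracket in 4.3.1.1 to 99.5°F, so that the limit reads >37.5°C (99.5°F). Section 3.1.4 stays as it is.
- **If 38.0°C was meant:** change the limit in both 4.3.1.1 and 3.1.4 to >38.0°C (100.4°F).

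Either change aligns the number only; the measurement route and the rescheduling wording of the two sections are untouched. In the likely case the cost is one bracketed number.

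If dosing is complete, a clarification note is enough. The SAP change history suggests that it is, without proving it: the entry of 09-Dec-2022 reads "Removed analyses for Month 3 boost (as no participants had the Month 3 boost".

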##### *4.3.1.2 Study Discontinuation*

Participants may choose to discontinue both treatment and study assessments. In this case, the Investigator or research worker should attempt to ascertain the reason for a participant's discontinuation of safety follow-up assessments, without compromising their right to withdraw at any time without giving a reason, and record this in the electronic Case Report Form (eCRF). Note that, unless the participant specifically revokes their earlier consent for information about

their progress, clinical information will continue to be collected and participant information will be retained in the trial database and used for intention-to-treat analyses of study outcome.

Participants **may** be withdrawn from the study in the event of:

- A severe adverse event or SAE
- Difficulties in obtaining blood or other samples
- Failure of the participant to comply with the protocol requirements or to cooperate with the Investigator

Participants **must** be withdrawn from the study in the event of:

- Withdrawal of consent

Participants will be withdrawn from study vaccination (if it has not yet been administered) in the event of:

- For safety reasons, it being in the best interest of the participant that he/she be withdrawn, in the Investigator's opinion
- A positive pregnancy test or if the participant is non-compliant with the contraception requirements (see [Section 4.2](#))
- Development of a medical condition that requires concomitant treatment with a potentially toxic therapy

#### ***4.3.2 Study Termination***

The study may be terminated, either at one centre or all centres for the following reasons:

- The discovery of an unexpected, serious or unacceptable risk to participants enrolled in the study
- The decision on the part of the Sponsor to suspend or discontinue testing, evaluation or development of ChAdOx1-HBV and MVA-HBV vaccines. In the event of the Sponsor's decision to no longer supply study vaccine, ample notification will be provided so that appropriate adjustments to treatment can be made.
- Serious failure of the Investigator to comply with ICH GCP [36] or local regulations
- Submission of knowingly false information from the study centre to the Sponsor, the independent ethics committee (IEC)/institutional review board (IRB) or regulatory authorities
- Major, repeated, non-adherence to the protocol

The Sponsor must be informed immediately in the event of any major protocol violation or serious breach of ICH GCP.

## 5 INVESTIGATIONAL MEDICINAL PRODUCTS

The Investigator must ensure that study vaccines and nivolumab are handled only by study team members who have been appropriately trained for the conduct of this clinical study and that dosing is only performed by study team members who fully understand the procedures outlined in this section, the Investigator's Brochure and the Pharmacy Manual. A Delegation of Authority Log will be maintained by the study centre and will identify the individual(s) authorised to prepare and administer the study vaccine.

### 5.1 Identity of Investigational Medicinal Products

#### 5.1.1 Study Vaccines

ChAdOx1-HBV is a genetically-modified (GM) non-replicating chimpanzee adenovirus vector encoding HBV consensus sequences from a group C genotype. The ChAdOx1 virus has been engineered to be replication deficient.

ChAdOx1-HBV is formulated in isotonic buffered saline comprising of 10 mM L-histidine, 35 mM NaCl, 7.5% sucrose (w/v), 1 mM MgCl2.6H2O, 0.1% (w/v) Polysorbate 80, 0.1 mM ethylenediaminetetraacetic acid, 0.5% ethanol (v/v), water for injections to 1 mL, pH 6.6 to a target concentration of  $1 \times 10^{11}$  vp/mL.

MVA-HBV is a GM poxvirus that is non-replicating in mammalian cells encoding the same HBV consensus sequences as ChAdOx1-HBV. The MVA virus is no longer able to replicate in humans and has safely been administered to over 130,000 people. It both boosts and prolongs the CD4+ and CD8+ T cells induced by ChAdOx1.

MVA-HBV is formulated in saccharose 50 g/L, 50 mM NaCl, 10 mM TRIS, 10 mM sodium glutamate, pH 8.0 to a target final concentration of  $2.0 \times 10^8$  pfu/mL.

The ChAdOx1-HBV and MVA-HBV vaccines will be supplied in glass vials. The vials are stoppered with sterilised European Pharmacopoeial/United States Pharmacopoeial Type 1 chlorobutyl and bromobutyl rubber stoppers respectively and sealed with aluminium/copolymer caps.

The study vaccines are manufactured to Good Manufacturing Practice and released by a qualified person.

